## 2. POWER CONSIDERATIONS

For the SF-36-PFS score (primary endpoint), a difference of 10 points is considered clinically significant. Similarly, in a study of CFS/ME which shares similarities with post-Covid syndrome, the minimally clinically important difference of SF-36-PFS was reported to be 10. The scatter of SF-36-PFS scores among post-Covid syndrome sufferers are unknown, but two large Norwegian surveys reported a Standard Deviation (SD) of 20 across all age groups. If SD is set to be 25 in the population under study, and assuming 20 % drop-out rate, the study should aim to **include a total of 310 participants**. This yields a power of 90 % ( $\alpha=0.05$ ) to detect a small to medium effect size.

### 3. ANALYSIS SETS

#### **Full analysis set**

The ‘full analysis set’ is defined as all patients who were included and randomised. This ‘full analysis set’ will be used for intention-to-treat analyses of efficacy. Missing values will be imputed based on the principle of multiple imputation, given a “missing-at-random”-pattern.

#### **Per protocol analysis set**

The ‘per protocol analysis set’ is defined as all patients in the ‘full analysis set’ that completed the treatment period and responded to the T1 questionnaire, without any of the following protocol deviations:

- Interruption of therapy.
- Lost to follow-up.
- Primary endpoint measurements missing.
- Diagnosed with another chronic disorder during the study period.
- Experiencing a severe illness or trauma during the study period.
- Commencing other treatment for post-COVID-19 condition during the study period.

Missing data will not be imputed in the per protocol analysis set.

### 4. STATISTICAL METHODS

#### **General considerations**

Continuous variables will be reported with parametric (mean/standard deviation) or non-parametric (median, quartiles) descriptive statistics, depending on the distribution.

Ordinal/nominal variables will be reported as frequency tabulation. All statistical tests will be carried out two-sided. A p-value  $\leq 0.05$  is considered statistically significant.

#### **Analyses of intervention effect**

Intention-to-treat analyses (full analysis set) will be used to compare the group allocated to intervention with the group allocated to routine follow-up using general linear models (ANCOVA) for the primary endpoint. Analogous methodology within the generalized linear method group of statistical modeling will be used for secondary endpoints that are not linear. The baseline values of each efficacy endpoint as well as stratification variable will be included as covariates. The null hypothesis is no differences in efficacy variables between the two treatment allocation groups. For each statistical analysis, the net intervention effect (the mean change in the intervention group minus the mean change in the routine follow-up group) will be estimated from the parameters of the fitted model and reported with 95 % confidence interval. An identical methodological approach will be applied for per protocol analyses based upon the per protocol analysis set.

Safety data will be summarized descriptively through appropriate data tabulations and descriptive statistics. No interim analysis will be carried out.

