1.1 Needs description

The present study addresses urgent needs for the health care services as well as the scientific community

- *Patient treatment.* This project directly addresses a strong need to develop effective treatment strategies for a large patient group suffering from post-Covid syndrome disability. Thus, it significantly improve health care services. Of note, the pragmatic approach ensures strong external validity and generalizability of the results.
- *Relevance and benefit to society.* This project addresses a highly challenging health problem nationally and internationally, which may have substantial negative impact upon employment issues, social security systems, family networks etc.
- *Scientific relevance.* The project addresses a prominent knowledge gap. Also, as the intervention builds upon a specific pathophysiological model, the study results will provide increased insight in disease mechanisms, and may eventually foster similar studies in PPIS following other infections.

2. Hypotheses, aims and objectives

We hypothesise that a short-time outpatient-based rehabilitation program will be beneficial as compared to usual care in post-Covid syndrome

The aim of the present study is to assess the efficacy of a short-time outpatient-based rehabilitation program (the intervention) as compared to usual care (non-intervention) in post-Covid syndrome. The objectives are:

- a) To determine the effect on physical functioning immediately after completion of the intervention. We hypothesises better physical functioning in the intervention group than in the non-intervention group.
- b) To determine the effect on other post-Covid syndrome symptoms (such as fatigue, cognitive difficulties, dyspnoea, pain, sleeping problems) and quality of life (QoL) immediately after completion of the intervention. We hypothesise a beneficial effect of the intervention across all these domains.
- c) To determine adverse effects of the intervention. We hypothesis no differences in the frequency nor seriousness of adverse effects in the intervention group as compared to the non-intervention group.
- d) To determine the effect of the intervention on a long-term basis. We hypothesise that a beneficial effect of the intervention is sustained six months after its delivery.

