### Effect monitoring

Effect monitoring is primarily based on patient reported outcome measures (PROM), applying a web-based questionnaire composed of several validated instruments. The questionnaire will be distributed to the participants at T0, T1 and T2. It will chart clinical symptoms as well as background, psychological and social variables, and will be used for subgrouping according to case definitions of post-COVID-19 syndrome and post-infective fatigue syndrome. The SF-36 subscale Physical Functioning (SF-36-PFS) score at T1 will serve as the **primary endpoint**.

Secondary endpoints include score of PROM inventories at T1 and T2, such as:

- *The Chalder Fatigue Questionnaire (CFQ)* charts subjective experience of physical and mental fatigue. In this study, the CFQ total linear score (i.e. the sum across all 11 items, each item scored on a zero to three Likert scale) will be applied. Furthermore, fatigue

caseness is defined as a CFQ total dichotomous score of 4 or higher (each item scored 0-0-1-1).

- *The Hospital Anxiety and Depression Scale (HADS)* is a validated questionnaire for charting symptoms of depression and anxiety. It consists of 14 items rated zero to three on Likert scales, allowing computation of sub-scores for depression and anxiety symptoms. In the present study, these sub-scores as well as total sum score will be applied.
- *Adverse effects*: A self-invented questionnaire will address possible adverse effect related to the intervention.

Cf. protocol with appendix for at detailed overview of inventories. In addition, employment status, usage of social security-systems (i.e. short and long-term sick leave), and usage of health care services (i.e. the number of GP and specialist contacts, hospitalisations, medications, usage of rehabilitation services, etc.) will be charted through register linkage (cf. below) as well as questionnaires to the study participants.

Also, recovery from post-infective fatigue syndrome will serve as an endpoint. The appendix of the present statistical analysis plan provides an operationalization of post-infective fatigue syndrome according to the Fukuda-definition within the context of the present study.

[figure not shown]

Figure 1. Overview of study design

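### Adverse effects are the subject of a between-arm hypothesis, but the SAP plans only a descriptive safety summary, with no between-arm estimate, confidence interval or named analysis set

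*SAP*

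**What the plan says.** Protocol section 2, objective c, is comparative: "We hypothesis no differences in the frequency nor seriousness of adverse effects in the intervention group as compared to the non-intervention group".

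The method for safety is one sentence, identical in the protocol (section 3.1, Statistical analyses) and in SAP section 4 (Analyses of intervention effect): "Safety data will be summarized descriptively through appropriate data tabulations and descriptive statistics". The protocol defers detail to a later SAP, but the SAP adds nothing on this point.

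SAP section 3 assigns the full analysis set to one purpose: it "will be used for intention-to-treat analyses of efficacy". It adds that "Missing values will be imputed based on the principle of multiple imputation". The per protocol set is used in section 4 to repeat the effect analyses. Neither set is assigned to safety.

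SAP section 1 (Effect monitoring) opens a list with "Secondary endpoints include score of PROM inventories at T1 and T2, such as", and one bullet of that list is adverse effects: "A self-invented questionnaire will address possible adverse effect related to the intervention".

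**The concern.** The objective compares the arms, but the analysis sentence does not commit to a comparison. A plan followed to the letter would give summaries of adverse effects without a prespecified statement of how large an excess in the intervention arm remains compatible with the data.

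The open analysis set matters as well. The per protocol set removes participants with interrupted therapy, severe illness or trauma, or a newly diagnosed chronic disorder, and some of these may be the participants who were harmed. With no set named, the denominator could be chosen after the data are seen. Participants know their allocation and the harm instrument is self-made, so fixing the comparison in advance is worth more here than usual.

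**Working it through.** **Step 1. Which rule governs adverse effects?** Two places in the SAP bear on this.

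- Section 1 lists adverse effects among secondary endpoints. Section 4 gives non-linear secondary endpoints generalised linear models and attaches a 95% confidence interval to the net effect in each analysis. Taken alone, this would provide a between-arm estimate.
- Section 4 also gives safety data their own descriptive sentence, and words the modelled analysis for efficacy: "The baseline values of each efficacy endpoint as well as stratification variable will be included as covariates", and "The null hypothesis is no differences in efficacy variables between the two treatment allocation groups". The estimate is a difference in mean change, yet no scale, scoring or baseline value is given for the adverse-effects questionnaire.

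The safety sentence is the more natural reading. The SAP does not say so, so the two sections need reconciling.

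**Step 2. Inputs for size.** 310 randomised 1:1 with 20% drop-out assumed (SAP sections 1 and 2): 310/2 = 155 per arm, or 310 × 0.8/2 = 124 per arm. The documents state no adverse-effect rate, so rates of 5%, 10% and 20%, equal in both arms, are assumed for illustration.

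**Step 3. The plan's own figure.** The only stated precision figure is 90% power for the primary endpoint (10 points, SD 25, two-sided 0.05). At 124 per arm: 10/(25 × √(2/124)) = 3.15; 3.15 − 1.96 = 1.19; power = 88%, close to the stated value. It says nothing about harms.

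**Step 4. Width of the missing interval.** The Wald 95% half-width for a risk difference with equal rates is 1.96 × √(2p(1−p)/n). For example, with p = 0.10 and n = 124: 1.96 × √(0.18/124) = 1.96 × 0.0381 = 7.5 points.

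| Assumed rate in both arms | 124 per arm | 155 per arm |
|---|---|---|
| 5% | ±5.4 points | ±4.9 points |
| 10% | ±7.5 points | ±6.7 points |
| 20% | ±10.0 points | ±8.9 points |

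**Step 5. Check with Newcombe intervals** (Wilson limits combined by square-and-add).

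- 12 v 12 of 124: each rate is 9.68%, with Wilson limits 5.62% to 16.16%. Half-width = √((9.68 − 5.62)² + (16.16 − 9.68)²) = 7.6 points.
- 16 v 16 of 155: ±7.0 points.
- No events in either arm: ±3.0 points at 124 per arm, ±2.4 at 155.

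Identical counts of about 10% per arm would therefore still be compatible with an excess of about 7 to 8 points.

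**The case against.** The strongest reply is that descriptive safety reporting is common and was chosen deliberately: the same sentence stands in both documents, and no test, margin or decision rule is attached to objective c. SAP section 4 (General considerations) also promises frequency tables for ordinal and nominal variables. In a two-arm trial with a comparative objective, tables by arm are the obvious expectation, and a reader could derive an interval from them. This stands in part. A reader might infer that objective c could be neither supported nor bounded under the plan. The documents do not support that: what is lost is prespecification and the assurance of usable denominators, not every means of bounding harm. Nor does the plan say that similar counts will be taken to show no difference; that is a misuse to guard against, not one it commits.

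A second reply is that the secondary-endpoint listing already brings adverse effects under the model. For the reasons in step 1 this reading is weak, and accepting it would still require the two sections to be reconciled.

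A third reply stands. A reader might assume that any-event and serious-event variables are already due to be collected. Neither the effect-monitoring sections nor the protocol's inventory appendix gives items, event definitions or a seriousness grading for the questionnaire. It also asks about effects related to the intervention, so it is unclear how usual-care participants would answer. A risk difference is meaningful only where the items can be answered alike in both arms.

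**Conclusion.** The point holds. A between-arm hypothesis on adverse effects has no planned estimate or interval to answer it, no analysis set is named, and the listing under secondary endpoints is not reconciled with the safety sentence.

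The size is illustrative. The half-widths of about 5 to 10 points rest on assumed equal rates of 5% to 20% and on 124 to 155 respondents per arm; other rates would change them. They show only that similar counts would be weak evidence for the hypothesis. The primary endpoint, its test and the sample size are unaffected. This is a worthwhile and cheap improvement to the plan, not a flaw that threatens its main conclusion.

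**What to change.** In SAP section 4:

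1. State that the safety sentence, not the mean-change model, governs adverse effects.
2. Report adverse effects by randomised arm, with counts and denominators, among all randomised participants who answered the items at T1 and, separately, at T2. Do not restrict to the per protocol set.
3. Add the between-arm risk difference with a 95% confidence interval (for example Newcombe) for any adverse effect. Do the same for serious adverse effects where the questionnaire or other collected data grade seriousness. Both apply only where the items can be answered alike in both arms.
4. Report the interval limits as the range of excess harm compatible with the data, and state that similar counts will not be taken as showing no difference, because no margin is set.

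The cost is a few sentences of SAP text, plus a check of what the questionnaire actually records; if it does not yield comparable events, item 3 shrinks accordingly. There are two downsides. The comparison will be visibly imprecise, and responder-only data may be biased if response differs by arm, which is why the denominators should be shown.

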#### **Subgroup analyses**

The outcome of the intervention in subgroups will be explored, based upon the full analysis set. Adherence to post-infective fatigue syndrome case definition at baseline (T0) will serve as the subgrouping variable. A differential outcome will be tested for efficacy variables at both time point, applying a generalized linear models including relevant interaction terms. Results of subgroup analyses will be presented if the interaction  $p < 0.10$ .

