- e) To explore predictors of intervention effect, including differential effects across subgroups. We hypothesise that time since diagnosis of acute Covid-19 and hospitalization is negatively associated with intervention effect. Furthermore, we hypothesise equal effect of the intervention in the subgroup fulfilling diagnostic criteria for chronic fatigue syndrome/myalgic encephalomyelitis (CFS/ME).
- f) To determine the cost-benefit and cost-effectiveness of the intervention. We hypothesise cost-benefit and cost-effectiveness to be better in the intervention as compared to the non-intervention group.

3. Project methodology

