3.3. Plan for activities, visibility and dissemination

A PhD-dissertation can be completed within three years from project onset; the entire project period is estimated at a maximum of 10 years

A PhD-fellow focusing on research questions a) – c) will be able to complete a dissertation within approximately three years from project onset. However, extensive analyses related to research questions d) – f) are estimated to take longer time, and is also dependent on external funding of additional researchers (PhD and/or postdoctoral positions). Thus, the total project period is estimated at a maximum of 10 years.

Results will be disseminated widely; scientific dissemination is prioritized

Given the seriousness of post-Covid syndrome and the urgent need for scientific knowledge, rapid and continuous dissemination of project results will receive high attention. The target for dissemination is not restricted to the scientific community, but includes a wide range of health-care workers, politicians, policy makers, health care administrators, and the general public.

Several means of dissemination will be exploited, including scientific papers; popular science newspaper articles; giving interviews; meetings with politicians, public health providers and other stakeholders; social media. Dissemination to researchers and the scientific community includes publications in international, peer-reviewed, open access medical journals. The main results will be offered to journals of high impact. Negative findings will also be reported.

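### Subgroup results are shown only when the interaction p-value is below 0.10, so if the hypothesised equal effect in CFS/ME is true, each result is withheld 90% of the time

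*SAP*

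**What the plan says.** Protocol section 2, objective e, sets out to explore predictors of the intervention effect and states a hypothesis: "we hypothesise equal effect of the intervention in the subgroup fulfilling diagnostic criteria for chronic fatigue syndrome/myalgic encephalomyelitis (CFS/ME".

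The SAP (section 4, Subgroup analyses) names one subgrouping variable: "Adherence to post-infective fatigue syndrome case definition at baseline (T0) will serve as the subgrouping variable". The SAP appendix defines this syndrome by modified Fukuda criteria. On scope the SAP says "A differential outcome will be tested for efficacy variables at both time point", using models with interaction terms. On reporting it says "Results of subgroup analyses will be presented if the interaction" p-value is below 0.10. No other sentence provides for presenting these results when the p-value is higher.

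Three other statements bear on the point:
- SAP section 4, General considerations: "All statistical tests will be carried out two-sided", with significance at 0.05.
- SAP section 2, for the SF-36 physical functioning score: "a difference of 10 points is considered clinically significant".
- Protocol section 3.3, in general terms: "Negative findings will also be reported".

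**The concern.** A hypothesis of equal effect is the null hypothesis of the interaction test. A rule that shows results only when that test gives a small p-value reports on the hypothesis mainly when the data appear to contradict it. When the hypothesis is right, the usual outcome is silence.

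There are two consequences. First, readers would usually see no estimate or interval, so they could not tell whether the data support similar effects or are merely imprecise. The SAP does not say that a p-value of 0.10 or more will be read as equal effect, but it gives the reader little else to go on. Second, the interactions that do appear have been selected for size and are too large on average. This is selective reporting on a stated objective. It does not touch the primary analysis.

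**Working it through.** **Inputs from the documents.** 310 randomised 1:1, SD 25, 20% dropout, important difference 10 points (SAP sections 1 and 2); two-sided tests and display at interaction p < 0.10 (SAP section 4). Completers: 310 × 0.80 = 248.

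**Assumed, because the documents give no figure.** Share of patients with baseline PIFS, π: 50%, with 20% or 80% at the extreme. Correlation of the score with its baseline, r: 0 to 0.5. Analysed N: 248 to 310.

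**The plan's own figures.** It gives none for the subgroup rule. For the main effect, 10 points with SD 25 at 90% power needs 132 per arm. With 124 completers per arm the power is 88.3%, close to the stated 90%. Nothing below depends on that claim.

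**Step 1: withholding under equal effect.** If the true interaction is zero, the p-value of a valid test is uniform, so P(p ≥ 0.10) = 1 − 0.10 = 0.90 per test. This needs no assumption about SD, N or split. Simulation of the interaction test (10,000 runs per setting, N of 248 and 310, subgroup share 20 to 70%) gave 0.894 to 0.903.

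**Step 2: precision.** SE = 25 × √(1 − r²) × √[4/(Nπ) + 4/(N(1 − π))].

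- Base case, N = 248, π = 0.5, r = 0: 25 × √(4/124 + 4/124) = 6.35.
- Most favourable, N = 310, π = 0.5, r = 0.5: 4.92.
- Least favourable, N = 248, π = 0.2, r = 0: 7.94.

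**Step 3: what the rule does to SF-36 physical functioning.**

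| Quantity | Base | Most favourable | Least favourable |
|---|---|---|---|
| Display threshold, 1.645 × SE (points) | 10.4 | 8.1 | 13.1 |
| 95% CI half-width, 1.96 × SE (points) | 12.4 | 9.6 | 15.6 |
| p-value for an observed 10 points, z = 10/SE | 0.115 | 0.042 | 0.208 |
| P(shown) if the true interaction is 10 | 47% | 65% | 35% |
| Mean estimate when shown, truth 10 (points) | 15.3 | 12.8 | 18.2 |
| Mean absolute estimate when shown, truth 0 (points) | 13.1 | 10.1 | 16.4 |

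With Φ and φ the standard normal distribution and density, P(shown) = Φ(10/SE − 1.645) + Φ(−10/SE − 1.645). In the base case 10/6.35 = 1.575, so P(shown) = Φ(−0.07) + Φ(−3.22) = 0.473. The means are those of a normal variable given that its absolute value exceeds the threshold. For truth 0 the mean is SE × φ(1.645)/0.05 = 2.063 × SE, which in the base case is 2.063 × 6.35 = 13.1.

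**Check by simulation.** 8,000 ANCOVA trials per setting, N = 248, 50/50 split. With no true interaction, 10.3% (r = 0) and 9.9% (r = 0.5) were shown. With a true 10 points, 46.6% and 56.8% were shown, with mean shown estimates of 15.5 and 13.8.

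**Step 4: many tests.** The SAP does not count the efficacy variables. For illustration, with 10 independent tests and no true interaction, at least one is shown with probability 1 − 0.9¹⁰ = 0.65, and what is shown is then chance. Correlated outcomes lower this figure without changing the mechanism.

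**The case against.** The strongest objections concern how firmly the text can be read.

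- **If or only if.** The SAP says results are presented if the condition is met. The rule could govern only the subgroup-specific effects, leaving the interaction test itself to be reported. That reading is possible but less natural: a display condition has no purpose unless results failing it are left out, and no other presentation is planned.
- **PIFS is not CFS/ME.** The link is inferred. It rests on the modified Fukuda definition, on the protocol's plan (section 3.1, Effect monitoring) to subgroup by CFS/ME case definitions, and on PIFS being the only subgroup the SAP names. The SAP appendix also defines caseness at 6 months, using fatigue scores at baseline and at 6 months, so caseness at T0 is not cleanly specified. That stands, and any reported table depends on resolving it.
- **Supporting contradictions are weak.** The commitment that the effect "will be estimated from the parameters of the fitted model and reported with 95 % confidence interval" concerns the comparison of allocation groups, not interactions. The promise about negative findings is general. Neither overrides the specific subgroup rule, and the finding does not need them.
- **The 10-point example is sensitive.** With N = 248 and a 50/50 split, a baseline correlation of 0.3 gives p = 0.099 for an observed 10 points, which would be shown. With N = 310 and no correlation, p = 0.078. Moreover, the documents give 10 points as an important difference in score, not as a margin between subgroup effects.
- **It is exploratory.** This is true, and the protocol expects the extensive analyses for objectives d to f to come later. That justifies cautious labelling but not leaving out the estimate.

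A reader holding the SAP could infer from silence that p was at least 0.10, but not where the estimate lies or how precise it is.

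**Conclusion.** The concern holds. Followed as written, the SAP withholds each interaction result 90% of the time when the protocol's hypothesis of equal effect is true. That figure follows from the rule itself and would be the same for any valid test screened at 0.10. How far the rule distorts SF-36 physical functioning depends on the assumed subgroup share, baseline correlation and analysed N, and a different choice can reverse whether an observed 10-point interaction is shown. The selection is present across the whole range: even in the most favourable case a true 10-point interaction goes unreported about a third of the time (100% − 65% = 35%). In the base case the 95% interval reaches 12.4 points either side of the estimate, so a p-value of 0.10 or more does not by itself show equal effect. The sponsor should change the rule, though the primary endpoint and main conclusion do not depend on it.

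**What to change.** In SAP section 4, Subgroup analyses:

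1. Delete the sentence that makes presentation depend on the interaction p-value.
2. For SF-36 physical functioning at T1 and T2, always report the treatment-by-PIFS interaction and both subgroup effects with 95% confidence intervals.
3. For every other efficacy variable tested, tabulate the interaction estimate with its 95% interval, labelled exploratory.
4. State that a non-significant interaction will not be read as equal effect. For SF-36 physical functioning, interpret the interval against the 10-point difference in SAP section 2, and say explicitly that this value is being used as the yardstick for a difference between subgroup effects.
5. State how PIFS caseness at T0 is derived, since the appendix defines it at 6 months.

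Optionally, report treatment-by-hospitalisation and treatment-by-time-since-infection interactions in the same way. Objective e names both, and the protocol already lists hospitalisation and the date of COVID-19 among its predictors.

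The cost is SAP wording and some extra table rows, with no new data. Precision does not improve, since it is set by the sample size, and the trial may have to describe the equal-effect question as inconclusive.
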